4.6.6.8.4. Definitions of Participant ADA Status

TE ADA-evaluable participants: A participant is evaluable for TE ADA if the participant has a nonmissing baseline ADA result and at least 1 nonmissing postbaseline ADA result.

TE ADA-unevaluable participant: any participant who does not meet the evaluable criteria.

Baseline ADA Present (preexisting antibody): ADA detected in a sample collected up to the first dose date and time.

Baseline ADA Not Present: ADA is not detected, and the corresponding PK concentration is missing or below the drug tolerance limit in a sample collected up to the first dose date and time.

TE ADA+ participant: An evaluable participant who had a:

- baseline status of ADA Not Present and at least 1 postbaseline status of ADA Present with titer $\ge 2 \times$ the MRD of the ADA assay.
- baseline and postbaseline status of ADA Present, with the postbaseline titer being 2 dilutions (4-fold) greater than the baseline titer. That is, the participant has baseline status of ADA Present, with titer 1:B, and at least 1 postbaseline status of ADA Present, with titer 1:P, with P/B ≥4.

As shown in Figure GPGV.4.1, a titer is expected when the ADA assay result is Detected. On the occasion, when the corresponding assay cannot be performed, in which case a titer value will be imputed for the purpose of TE ADA determination. A baseline sample with detected ADA and no titer is imputed to be the MRD (1:10), and a postbaseline sample with ADA detected and no titer is imputed to be 1 dilution above the MRD (1:20).

TE ADA-Inconclusive participant: A TE ADA evaluable participant is TE ADA Inconclusive if ≥20% of the participant's postbaseline samples, drawn predose, are ADA Inconclusive and all remaining postbaseline samples are ADA Not Present.

TE ADA-negative (TE ADA-) participant: A TE ADA-evaluable participant is TE ADA- when the participant is not TE ADA+ and not TE ADA Inconclusive.

For each NAb assay, the following are defined:

NAb+ participant: A participant who is TE ADA+ and has a NAb+ sample in the postbaseline period.

NAb Inconclusive participant: A participant who is TE ADA+ but not NAb+, and all samples that have TE ADA+ titer have a NAb Inconclusive sample result.

Nab negative (NAb-) participant: A participant is who is neither NAb+ nor NAb Inconclusive.

Unless specified otherwise, the above-mentioned definitions of NAb are applicable to all NAb analyses, including cross-reactive NAb analyses and cross-reactive antibodies.

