	If drug concentration was planned but is not available for a treatment-period sample, a Not Detected sample will be declared ADA Not present.	
ADA Inconclusive	ADA assay result is Not Detected but drug concentration in the sample is	
	≥ the assay's drug tolerance level, which may cause interference in the ADA	
	detection method.	
ADA Missing	ADA sample not drawn, QNS, not tested, etc., causing there to be no	
	laboratory result reported or the result is reported as "no test."	

Abbreviation: ADA = antidrug antibodies; QNS = quantity not sufficient.

All ADA present samples will be evaluated for cross-reactive GIP (Tier 2b), cross-reactive GLP-1 (Tier 2c), NAb LY (tirzepatide) on GIP-R (Tier 4a), and NAb LY (tirzepatide) on GLP-1R (Tier 4b).

Similar terminology to Table GPGV.4.7 applies for each type of cross-reactive and NAb assay. Importantly, each of these are distinct assays and, in general, have different assay operating characteristics.

The following are considered inconclusive for the NAb result:

• NAb LY on the GIP-R: If the NAb result is not detected and the pharmacokinetic (PK) concentration is ≥ drug tolerance limit of the NAb LY on the GIPR assay,

• NAb LY on the GLP-1R: If the NAb result is not detected and the PK concentration is ≥ drug tolerance limit of the NAb LY on the GLP-1R assay.

For cross-reactive NAb interpretations against native GIP and GLP-1, an *in silico* method utilizing results from Tiers 2b and 2c, Tiers 4a and 4b, and tirzepatide concentrations is introduced. The *in silico* method is outlined in Table GPGV.4.7.

Table GPGV.4.7. In Silico Classification for Cross-Reactive NAb

In Silico Classification	Cross-Reactive ADA Result	NAb Result	Circulating Tirzepatide Level (ng/mL)	In Silico Cross-Reactive NAb Interpretation
Cross-Reactive NAb to nGIP	Tier 2b: "Not detected"	Tier 4a: "Not Detected" or Tier 4a: "Detected," N/A, or Missing	Any value or missing	Not Present
	Tier 2b: "Detected"	Tier 4a: "Not Detected"	< drug tolerance limit of the assay	Not Present
	Tier 2b: "Detected"	Tier 4a: "Not Detected"	≥ drug tolerance limit of the assay	Inconclusive
	Tier 2b: "Detected"	Tier 4a: "Detected"	< drug tolerance limit of the assay	Present
	Tier 2b: "Detected"	Tier 4a: "Detected"	≥ drug tolerance limit of the assay	Present
Cross-reactive NAb to nGLP-1	Tier 2c: "Not detected"	Tier 4b: "Not Detected" or Tier 4b: "Detected," N/A, or Missing	Any value or missing	Not Present

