GLP-1R, GIP Cross-Reactive, In Silico Neutralizing to Native Treatment, LY	
GIP, GLP-1 Cross-Reactive and In Silico Neutralizing to Treatment Plus	
Native GLP-1 Present at baseline, Postbaseline TE ADA+, Follow-up)	
Neutralizing TZP for GIPR, GIPR Inconclusive, GLP-1R,	
GLP-1R Inconclusive, GIP Cross-Reactive, GLP-1 Cross-	
Reactive	
Summary of TE ADA Within the participants evaluable for TE ADA, the count and Immunogenicity	
Persistence for all TE ADA percentages of the following will be summarized: Analysis Set 2 (LY	Υ
Evaluable Tirzepatide- Persistence (Persistent, Potential Persistent, Transient) of Treatment, LY	
Treated Participants TE ADA+ participants, TE ADA- patients Treatment Plus	
Follow-up)	
Maximum Titer Distribution The distribution of the maximum titer values for the Immunogenicity	
of TE ADA+ Participants TE ADA+ participants will be summarized. Analysis Set 2(LY)	
Treatment)	1
· ·	
Summary of Time to First TE A summary table of time to first TE ADA+ titer in TE ADA Immunogenicity	
ADA+ Titer among evaluable participants will be examined by study and Analysis Set 2 (LY	·Υ
Tirzepatide-Treated TE ADA treatment group via cumulative categories (≤ 4 week, ≤ 12 Treatment)	
Evaluable Participants week, \leq 30 week, \leq 42 week, \leq 52 week, and \leq 56 week).	
Summary of Change of Analyses on the primary endpoint (change in HbA1c from Immunogenicity	
Tirzepatide-Treated baseline at Week 30), guided by the efficacy estimand, will be Efficacy Set	
Participants in HbA1c from presented visually in the form of boxplots and will include	
Baseline at Primary Visit by summary statistics for subgroups using TE ADA Status and	
TE ADA Status neutralizing TZP against GIPR and GLP-1R.	

Abbreviations: ADA = antidrug antibodies; GIP = glucose-dependent insulinotropic polypeptide; GIP-1 = glucose-dependent insulinotropic polypeptide receptor; GLP-1R = glucagon-like peptide-1 receptor; HbA1c = glycated hemoglobin; Nab = neutralizing antibodies; TE = treatment-emergent; TE ADA = treatment-emergent antidrug antibodies; TZP = tirzepatide.

Safety analysis:

A summary will be provided of the count and percentage of tirzepatide-treated participants experiencing specific TEAEs (Hypersensitivity reactions [see Section 4.6.6.6], Injection site reactions [see Section 4.6.6.7]) by participant TE ADA status (TE ADA+, TE ADA-, and TE ADA Inconclusive). These summaries will utilize data from Immunogenicity Analysis Sets 1. and 2 (LY Treatment).

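### SAP 4.6.6.8.4: a low-titre positive sample moves a participant from TE ADA Inconclusive to TE ADA-negative, and NAb-negative is a remainder not confined to TE ADA+

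*SAP*

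**What the plan says.** **Sample level (SAP 4.6.6.8.1, Table GPGV.4.6).** There are four statuses:

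- ADA Present: any Detected result, with no titre threshold.
- ADA Not Present: Not Detected, with drug below the assay's tolerance level or treated as such.
- ADA Inconclusive: Not Detected, with drug at or above that level.
- ADA Missing: "ADA sample not drawn, QNS, not tested, etc".

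**Participant level (SAP 4.6.6.8.4).**

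- Evaluable: a "nonmissing baseline ADA result and at least 1 nonmissing postbaseline ADA result".
- TE ADA+ from a negative baseline: "at least 1 postbaseline status of ADA Present with titer" of at least twice the minimum required dilution (MRD).
- TE ADA+ from a positive baseline: a later Present sample "with the postbaseline titer being 2 dilutions (4-fold) greater than the baseline titer".
- TE ADA Inconclusive: at least 20% of the "postbaseline samples, drawn predose, are ADA Inconclusive and all remaining postbaseline samples are ADA Not Present".
- TE ADA-: "A TE ADA-evaluable participant is TE ADA- when the participant is not TE ADA+ and not TE ADA Inconclusive".
- NAb+ and NAb Inconclusive both require TE ADA+. NAb- is any participant who is "neither NAb+ nor NAb Inconclusive".

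The section ends by carrying the NAb definitions over to the cross-reactive analyses unless stated otherwise.

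**Use (SAP 4.6.6.8.5).** The three TE ADA groups are tabulated. Hypersensitivity and injection-site reactions are summarised by TE ADA group. Week 30 HbA1c change is shown as boxplots by TE ADA status and by neutralizing status against each receptor.

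**The concern.** The Inconclusive label exists to keep participants whose antibody result may be masked by drug out of the negative group. Its second condition allows only one kind of companion sample, ADA Not Present. A companion sample in which antibody was detected, but below the treatment-emergent titre, breaks the condition. Because TE ADA- is defined by exclusion, the participant then lands there. The label therefore becomes more negative as the evidence of antibody grows.

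The NAb definitions have a similar weakness from a separate cause. NAb- needs no negative NAb result, only failure to meet two definitions that are both closed to anyone who is not TE ADA+.

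At stake is the purity of the TE ADA- comparator in the two adverse-event summaries and of the TE ADA and NAb groups in the HbA1c boxplots. Participants of unresolved status would dilute those groups, and the reported inconclusive count would be too low.

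**Working it through.** No figure in the plan needs reproducing; this is a check of the classification logic.

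**1. Thresholds.** The SAP's titre imputation rule gives the MRD as 1:10.

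- Negative baseline: TE ADA+ needs 2 × 10 = 20, so 1:20 or higher. Present at 1:10 falls short.
- Positive baseline at 1:10: TE ADA+ needs 4 × 10 = 40, so 1:40 or higher. A later 1:20 gives 20/10 = 2, which falls short.
- An untitred postbaseline detection is imputed as 1:20. That is TE ADA+ after a negative baseline, but only a two-fold rise over a baseline imputed at 1:10.

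**2. Labels.** Protocol 1.3.1 schedules double-blind postbaseline immunogenicity samples at Weeks 4, 12 and 30. Assume all are predose.

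| Week 4 / 12 / 30 | Inconclusive share | Rest all Not Present? | Label |
|---|---|---|---|
| Inconclusive / Inconclusive / Inconclusive | 3/3 | none left | Inconclusive |
| Not Present / Inconclusive / Inconclusive | 2/3 | yes | Inconclusive |
| Low-titre Present / Inconclusive / Inconclusive | 2/3 | no | TE ADA- |
| Missing / Inconclusive / Inconclusive, Missing counted | 2/3 | no | TE ADA- |
| Missing / Inconclusive / Inconclusive, Missing dropped | 2/2 | none left | Inconclusive |

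Rows two and three are the defect. With 5 scheduled samples (to Week 52) or 6 (with follow-up), one low-titre Present sample and the rest Inconclusive again gives TE ADA-, whichever way Missing is handled.

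**3. How many patterns.** Take three samples, each sub-threshold Present, Not Present, Inconclusive or Missing. Patterns with no Not Present sample number 3³ = 27. Of these, 2³ = 8 have no Inconclusive sample, leaving 27 − 8 = 19.

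- Missing counted as a sample: only the all-Inconclusive pattern is labelled Inconclusive, so 18 of 19 are TE ADA-.
- Missing dropped: patterns made only of Inconclusive and Missing, with at least one Inconclusive, number 2³ − 1 = 7 and are labelled Inconclusive. The other 19 − 7 = 12 are TE ADA-, and each contains a low-titre Present sample.

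These count possible patterns, not participants, and they exclude Not Present patterns by construction.

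**4. NAb.** A TE ADA Inconclusive participant is not TE ADA+, so can be neither NAb+ nor NAb Inconclusive, and is therefore NAb-. A TE ADA+ participant with no NAb result has no NAb+ sample and no NAb Inconclusive results, and is also NAb-. Changing the Inconclusive rule alone leaves both outcomes in place.

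**5. What moves.** The TE ADA+ and evaluability definitions do not refer to the Inconclusive rule, so TE ADA+ incidence keeps its numerator and denominator. At 90/3 = 30 per arm, all evaluable, one relabelled participant shifts the TE ADA- and Inconclusive rows by 1/30 = 3.3 percentage points in opposite directions.

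**The case against.** The low-titre route is narrow. After a negative baseline it needs a titre below 1:20, and untitred detections are imputed to the TE ADA+ side. After a positive baseline, an unboosted titre is by definition not treatment-emergent. Immunogenicity samples are taken predose where possible (Protocol 8.8), the tolerance limits are not given, and nothing shows that Inconclusive samples are expected. The three TE ADA groups are already reported separately, and Table GPGV.4.9 lists no NAb-negative row. The analyses concerned are descriptive or supportive.

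All of this limits the size, and it stands. It does not answer the ordering. An unboosted titre in one sample does not exclude a boost hidden in the masked samples, and that is the uncertainty for which the participant with a Not Present sample is called Inconclusive.

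Stronger readings are tempting but not supported:

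- *Anyone without a conclusive negative sample is called TE ADA-.* Not so: when every sample is Inconclusive, both conditions are met.
- *A single missing sample removes the Inconclusive label.* This follows only if Missing counts as a remaining sample. An undrawn sample hardly can; for insufficient or untested samples the SAP is silent. The figure of 18 of 19 rests on that reading.
- *TE ADA incidence is understated.* The TE ADA+ count does not change.
- *NAb status groups the adverse-event summaries.* They are grouped by TE ADA status only; NAb grouping enters the HbA1c boxplots, which are restricted to Week 30 completers.

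**Conclusion.** The point holds in a limited form and is minor. Followed exactly, SAP 4.6.6.8.4 labels a participant with at least 20% Inconclusive samples and one sub-threshold Present sample as TE ADA-, and labels the same participant Inconclusive if that sample is Not Present. The handling of missing and insufficient samples is unstated. Separately, NAb- takes in TE ADA Inconclusive participants and TE ADA+ participants without a NAb result.

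The consequences are confined to the TE ADA-/Inconclusive split, the TE ADA- comparator in the hypersensitivity and injection-site summaries, and the TE ADA and NAb groups in the HbA1c boxplots. The primary analysis and type I error are untouched. The number of participants affected cannot be estimated from the documents. Masking is a possibility the SAP itself raises in 4.6.6.8.1, and doses escalate after Week 4 (Protocol 6.5.1), so an early low-titre positive followed by masked samples is possible; its frequency depends on the undisclosed tolerance limits.

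**What to change.** In SAP 4.6.6.8.4:

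- Define TE ADA Inconclusive as evaluable, not TE ADA+, and with at least 20% of non-missing predose postbaseline samples ADA Inconclusive. Delete the condition on the remaining samples. This also settles how missing and insufficient samples count.
- Define NAb- only among TE ADA+ participants with at least one valid NAb Not Detected result, meaning one that is not itself inconclusive because of drug level.
- Show TE ADA+ participants with no NAb result as NAb not evaluable. Also state where a TE ADA+ participant goes whose NAb results are partly inconclusive and otherwise missing; NAb Inconclusive is the simplest place.
- Apply the same wording to the cross-reactive analyses and state the NAb denominator in Table GPGV.4.9.

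The cost is a few sentences and a small programming change. The only downside is that slightly more participants will be shown as inconclusive or not evaluable.

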4.6.6.8.5. Analyses to be Performed

Table GPGV.4.9 provides the list of planned core and efficacy immunogenicity analyses.

Table GPGV.4.9. List of Core and Efficacy Immunogenicity Analyses

Summary of TE Tirzepatide Anti-Drug Antibodies Status in Tirzepatide-Treated Participants evaluable for TE ADA ADA Present at baseline and NAb Present at baseline, TE ADA+, TE ADA Inconclusive, and TE ADA-, Treatment-induced TE ADA+ and treatment-boosted TE ADA+, Treatment Plus Follow-up) TE ADA+ with NAb Present postbaseline, and TE ADA+ without NAb Present postbaseline but having NAb	
in Tirzepatide-Treated Participants Summarized: Participants evaluable for TE ADA ADA Present at baseline and NAb Present at baseline, Analysis Set 2 (LY TE ADA+, TE ADA Inconclusive, and TE ADA-, Treatment, LY Treatment-induced TE ADA+ and treatment-boosted TE ADA+, TE ADA+ with NAb Present postbaseline, and Summarized: Immunogenicity Analysis Set 2 (LY Treatment, LY Treatment Plus Follow-up)	
Participants Participants evaluable for TE ADA ADA Present at baseline and NAb Present at baseline, TE ADA+, TE ADA Inconclusive, and TE ADA-, Treatment, LY Treatment-induced TE ADA+ and treatment-boosted TE ADA+, TE ADA+ with NAb Present postbaseline, and Immunogenicity Analysis Set 2 (LY Treatment, LY Treatment Plus Follow-up)	
ADA Present at baseline and NAb Present at baseline, TE ADA+, TE ADA Inconclusive, and TE ADA-, Treatment, LY Treatment-induced TE ADA+ and treatment-boosted TE ADA+, Treatment Plus Follow-up) TE ADA+ with NAb Present postbaseline, and	
TE ADA+, TE ADA Inconclusive, and TE ADA-, Treatment, LY Treatment-induced TE ADA+ and treatment-boosted TE ADA+, Treatment Plus Follow-up) TE ADA+ with NAb Present postbaseline, and	
Treatment-induced TE ADA+ and treatment-boosted TE ADA+, TE ADA+ with NAb Present postbaseline, and Treatment Plus Follow-up)	Υ
ADA+, TE ADA+ with NAb Present postbaseline, and	
TE ADA+ with NAb Present postbaseline, and	
TE ADA+ without NAb Present postbaseline but having NAb	
Inconclusive at the follow up visit.	
Summary of Cross-Reactive Within the participants evaluable for TE ADA, the count and Immunogenicity	
and Neutralizing Antibodies percentage of participants with the following will be Analysis Set 1	
from Tirzepatide-Treated summarized:	
Participants with TE ADA Participants evaluable for TE ADA Immunogenicity	
ADA, Neutralizing TZP for GIPR, Neutralizing TZP for Analysis Set 2 (LY	Υ
GLP-1R, GIP Cross-Reactive, In Silico Neutralizing to Native Treatment, LY	
GIP, GLP-1 Cross-Reactive and In Silico Neutralizing to Treatment Plus	
Native GLP-1 Present at baseline, Postbaseline TE ADA+, Follow-up)	
Neutralizing TZP for GIPR, GIPR Inconclusive, GLP-1R,	
GLP-1R Inconclusive, GIP Cross-Reactive, GLP-1 Cross-	
Reactive	
Summary of TE ADA Within the participants evaluable for TE ADA, the count and Immunogenicity	
Persistence for all TE ADA percentages of the following will be summarized: Analysis Set 2 (LY	Υ
Evaluable Tirzepatide- Persistence (Persistent, Potential Persistent, Transient) of Treatment, LY	
Treated Participants TE ADA+ participants, TE ADA- patients Treatment Plus	
Follow-up)	
Maximum Titer Distribution The distribution of the maximum titer values for the Immunogenicity	
of TE ADA+ Participants TE ADA+ participants will be summarized. Analysis Set 2(LY)	
Treatment)	1
· ·	
Summary of Time to First TE A summary table of time to first TE ADA+ titer in TE ADA Immunogenicity	
ADA+ Titer among evaluable participants will be examined by study and Analysis Set 2 (LY	·Υ
Tirzepatide-Treated TE ADA treatment group via cumulative categories (≤ 4 week, ≤ 12 Treatment)	
Evaluable Participants week, \leq 30 week, \leq 42 week, \leq 52 week, and \leq 56 week).	
Summary of Change of Analyses on the primary endpoint (change in HbA1c from Immunogenicity	
Tirzepatide-Treated baseline at Week 30), guided by the efficacy estimand, will be Efficacy Set	
Participants in HbA1c from presented visually in the form of boxplots and will include	
Baseline at Primary Visit by summary statistics for subgroups using TE ADA Status and	
TE ADA Status neutralizing TZP against GIPR and GLP-1R.	

Abbreviations: ADA = antidrug antibodies; GIP = glucose-dependent insulinotropic polypeptide; GIP-1 = glucose-dependent insulinotropic polypeptide receptor; GLP-1R = glucagon-like peptide-1 receptor; HbA1c = glycated hemoglobin; Nab = neutralizing antibodies; TE = treatment-emergent; TE ADA = treatment-emergent antidrug antibodies; TZP = tirzepatide.

Safety analysis:

A summary will be provided of the count and percentage of tirzepatide-treated participants experiencing specific TEAEs (Hypersensitivity reactions [see Section 4.6.6.6], Injection site reactions [see Section 4.6.6.7]) by participant TE ADA status (TE ADA+, TE ADA-, and TE ADA Inconclusive). These summaries will utilize data from Immunogenicity Analysis Sets 1. and 2 (LY Treatment).

4.6.6.9. Hepatobiliary Disorders

4.6.6.9.1. Hepatobiliary Events

The detailed search criteria for hepatobiliary disorders can be found in Appendix 1. The counts and percentages of participants with treatment-emergent potentially drug-related hepatobiliary events will be summarized by treatment using the MedDRA PTs contained in the following 2 categories, separately:

- Hepatic events
- Acute gallbladder diseases.

Severe/serious hepatic events and severe/serious acute gallbladder disease will be considered as AESIs and summarized separately.

4.6.6.9.2. Liver Enzymes

This section describes additional analyses of liver enzymes. The following will be provided by treatment group:

- A shift table of maximum-to-maximum alanine aminotransferase measurement from baseline to postbaseline. Baseline categories include ≤1 × ULN, >1 to <3 × ULN, ≥3 to <5 × ULN, and missing. Postbaseline categories include ≤1 × ULN, >1 to <3 × ULN, ≥3 to <5 × ULN, ≥5 to <8 × ULN, ≥8 × ULN.
- A shift table of maximum-to-maximum aspartate transaminase measurement from baseline to postbaseline. Baseline categories include ≤1 × ULN, >1 × ULN to <3 × ULN, ≥3 to <5 × ULN, and missing. Postbaseline categories include ≤1 × ULN, >1 to <3 × ULN, ≥3 to <5 × ULN, ≥5 to <8 × ULN, ≥8 × ULN.
- Shift tables of maximum-to-maximum total bilirubin and direct bilirubin from baseline to postbaseline with the following categories: $\le 1 \times ULN$, >1 to $<2 \times ULN$, $\ge 2 \times ULN$.
- Shift tables of serum alkaline phosphatase from baseline to postbaseline with the following categories: $\le 1 \times ULN$, >1 to $<2 \times ULN$, $\ge 2 \times ULN$.

Maximum baseline will be the maximum non-missing observation in the baseline period. The maximum postbaseline value will be the maximum non-missing value from the postbaseline period. Planned and unplanned measurements will be included.

An MMRM as described in Section 4.1.5.4 will be used to fit the changes from baseline in these hepatic enzymes (ALT, AST, ALP, total bilirubin and direct bilirubin) for double-blind period

using SS1 and for overall study (double-blind, open-label, and follow-up periods) using SS2. Both units will be analyzed using log transformation.

4.6.6.10. Gastrointestinal Adverse Events

The PTs under the *Gastrointestinal disorders* SOC in MedDRA will be used to identify GI AEs, and only the PTs with serious/severe treatment-emergent cases will be considered as AESIs.

Summaries of all events of TE GI AE, including nausea, vomiting, and diarrhea will be provided by treatment and PT with decreasing frequency.

The time courses of prevalence and incidence (newly occurring episodes) of GI AEs (nausea and/or vomiting and/or diarrhea) will be plotted by treatment and maximum severity.

The maximum severity of TE nausea and/or vomiting and/or diarrhea through the end of the study will be summarized by treatment using SS1 from baseline to Week 30 and using SS2 from baseline to safety follow-up. Time to the onset of nausea, vomiting, and diarrhea will be plotted.

